**Sponsor/Funding Source:**

### **1. Purpose:**

Urinary tract infections (UTIs) are the most common bacterial infection in women. According to current guidelines, typical treatment consists of a short course of culture-proven antibiotics; however, UTIs can relapse. Recurrent UTIs (RUTIs) can be detrimental to the patient's health by increasing the chance of a UTI complication, such as potentially life-threatening sepsis (urosepsis) or permanent kidney damage from pyelonephritis. In addition, every time a UTI occurs, the patient will experience bothersome symptoms of urinary frequency and burning on urination and require prompt antibiotic treatment to eliminate the infection. Such repeated exposure to antibiotics can lead to adverse side-effects from the antibiotics used as well as an increase the development of antibiotic resistance. For patients with RUTIs, **there is a need to consider a prophylactic approach to lessen the frequency and severity of these recurrent episodes.**

Various prophylactic agents against UTIs have been studied, such as estrogen, cranberry juice/tablets, acupuncture, probiotics, and antiseptics, which differ from antibiotics in that they can affect a variety of microorganisms as opposed to just bacteria. Hiprex (methenamine hippurate) is one of the most popular antiseptics prescribed for RUTIs. Hiprex has been around for nearly a century, yet limited information is known on its exact mechanism of action in the urine and there are no strategies in place to target its use to each treated individual. Furthermore, despite several trials against different daily antibiotic prophylaxis, its role in the management of RUTIs has not been solidly established. Methenamine hippurate functions by producing formaldehyde, which inhibits bacterial growth [cit, Validus]. Previous studies have shown a modest decrease in the rate of re-infection in women with RUTIs after beginning Hiprex compared to the rate prior to initiating the medication; however, these studies have failed to produce meaningful results regarding women with RUTIs who do not have a complicated infection involving urinary catheters for example. Hiprex metabolism and excretion in the urine has been studied in the 60's, 70's and 80's. Although it is known that **formaldehyde production is enhanced by an acid environment**, urinary pH has not been routinely tested in patients who take this medication, a regrettable oversight which might affect the efficacy of this compound in vivo.

Therefore, the purpose of this study is to measure the concentration of formaldehyde in the urine of women with RUTIs on Hiprex; and then, assuming its urinary presence is confirmed at the

proper acid urinary pH, evaluate if such a therapy has favorable effects in decreasing the rate of RUTIs over time.

## 2. Background:

UTIs contribute to about 25% of all infections worldwide. In the US alone, UTIs incurred an estimated societal cost, including health care costs and productivity losses, of \$3.5 billion in 2015. Women are especially likely to contract UTIs compared to men at a ratio of 8:1 and have a 50-60% chance of experiencing at least one UTI in their lifetime. Almost a quarter of these UTIs will recur within the next 6 months. Risk factors of RUTIs include medical conditions, such as pregnancy, diabetes, immunosuppression, and abnormal urinary tracts; however, women without any of these comorbidities are still at risk of RUTIs. While recurrence is already a complication of UTIs, other complications can arise including acute renal failure or multi-organ system involvement with progression into bacteremia and then life-threatening sepsis and shock.

Treatment of RUTIs does not differ greatly from the treatment of their uncomplicated counterparts in that both still require culture-based antibiotics. However, patients with frequent UTIs will require repeated courses of antibiotics, a process which in time exposes to adverse side-effects from the medication and enhances the risk of antibiotic resistance. Thus, in patients with a history of RUTIs, prophylaxis should be considered once the treatment of the active UTI has been completed.

**RUTI prevention has been attempted via** lifestyle modifications and/or supplements. By drinking at least 2-3 liters of fluids a day and voiding frequently, patients will be able to eliminate bacteria from their urinary tracts. Reducing the number of new sexual partners will also decrease the risk of UTIs as will proper hygiene around the time of intercourse. Women are encouraged to wipe from front to back to limit the number of bacteria tracking from the anal and genital areas to the urethra. Prophylactic agents can take many forms. Aside from treatment of active infections, low-dose antibiotics (most commonly taken daily or post-coitally) have been shown to be effective at preventing UTIs; however, they still expose to the risks of antibiotic resistance and/or allergies. Vaginal estrogens have been shown to decrease the rate of UTIs by decreasing vaginal wall atrophy and conferring an unfavorable environment for the colonization of uropathogens with little worry of systemic absorption. Estrogen, along with probiotics, also increase the proliferation of beneficial bacteria like *Lactobacillus*, an important aspect of the natural genito-urinary microbiome protective mechanism. In animal models, D-mannose and cranberry juice/tablets have been found to block receptors that allow bacteria to attach to the bladder wall thus limiting colonization. However, despite having moderate efficacy against RUTIs, long-term adherence to D-mannose treatment was found to be questionable and the amount of D-mannose or cranberry realistically reaching the urinary bladder after an oral intake remains questionable and under study.

**Hiprex (methenamine hippurate) is one of the most widely prescribed antiseptics for the prophylaxis of RUTIs**[cit]. Earliest recorded usage of methenamine as a urinary antiseptic was described in 1899. Methenamine is hydrolyzed to ammonia and formaldehyde, which is bacteriostatic or bactericidal depending on its concentration. The rate of this hydrolysis was found to be greater in solutions with lower pHs, achieving formaldehyde concentrations of clinical use at prescription dosage when the pH was less than 6.0. Although the urine pH range varies from 5 to 8, a recent study from our group in post-menopausal women identified an average urine pH around 6.0 with daily variability in several patients, possibly related to diet intake. Furthermore, as methenamine is hydrolyzed, the production of ammonia alkalinizes the solution, slowing down the reaction. Thus, in 1961, in order to increase efficacy, its formulation with adding hippurate, which increases the acidity of urine, as Hiprex, was developed.

**A literature review on the metabolism and urinary excretion of methenamine produced sparse results.** Studies by Gollamudi and Strom detailed the use of silica cartridges to determine the concentration of methenamine and formaldehyde in a solution and test this new method on human urine after administration of Hiprex to subjects. However, this work has limitations, since only 11 participants were tested and the urine samples were only taken after the first dose of Hiprex rather than after several days or months of Hiprex intake. Strom also analyzed the kinetics of methenamine, finding that a methenamine concentration of 750 µg/mL at pH 6.0 could produce bactericidal concentrations of formaldehyde after 3 hr and that the hydrolysis of methenamine occurred 20 times faster at a pH of 5.0 versus 6.0^14. Another study determined that the concentration of formaldehyde in urine adequate to produce a bacteriostatic effect (25 µg/mL) could be attained by adding 0.6 mg/mL of methenamine to urine at a pH ≤ 5.7 or 1 mg/mL at pH ≤ 5.85. Because the two latter experiments produced their results *ex vivo*, the rate of excretion of methenamine into the urine and the proof of its metabolism of conversion to formaldehyde in a patient's urine after an oral intake of 1 gm twice a day as currently recommended remains untested.

There are **several studies reporting on the efficacy of Hiprex**; however, most only include patients with specific comorbid conditions. After excluding men, Table 1 includes a review of these studies. A case series found that the administration of Hiprex resulted in a decrease in catheter changes among patients with indwelling catheters. Another long-term study reported that, after starting Hiprex, a decrease in the rate of reinfection of UTIs in geriatric patients hospitalized was noted at two years, especially in those who were supervised while taking their medications; however, the rate of UTIs prior to starting Hiprex was not given. A review of Hiprex, containing 2032 patients across 13 studies, indicated that short-term treatment (1 week or less) of Hiprex in women without renal tract abnormalities led to a significant decline in UTIs. However, the authors admitted that given the heterogeneity in the populations studied and the outcomes measured, there was no clear consensus amongst these studies.

Although the literature offers no recommendation for the length of time to prescribe Hiprex, the current knowledge on Hiprex suggests a possible role of longer courses to fully evaluate its

efficacy in the management of RUTIs. Fortunately, many women evaluated for RUTIs will not have any of the examined comorbid conditions as listed in Table 1, and many will present without an overt risk factor for UTIs; thus, it is important to include these women in future studies.

**Hiprex can cause various mild side-effects**, such as rashes, diarrhea, sore throat, abdominal pain, and bladder “stinging”. Although the side-effects are typically self-limited and non-severe, hemorrhagic cystitis was found in the case of an accidental ingestion of 8 g of methenamine mandelate by a 2½-year-old. Despite the side-effect being due to a different formulation of methenamine from Hiprex as well as the dose being much higher than the recommended maximum of 500 mg, this rare case still underlines the importance of ensuring that Hiprex is effective enough so that its benefit outweighs its potential risks.

In summary, RUTIs can be debilitating in a large proportion of women. Despite the popularity of Hiprex as an RUTI prophylactic agent, there are still **large gaps of knowledge** regarding its use. Among them are its *in vivo* metabolism, including the measurements of urinary excretion of both methenamine and formaldehyde, the optimization of urine pH under 6.0 to enhance Hiprex presumed mechanism of action, and on the clinical side, the effectiveness and safety of Hiprex in geriatric patients as well as those with comorbidities, along with its cost-effectiveness over other long-term prophylactic agents for RUTI management.

Table 1: Literature review on the effect of Hiprex (HX) in women

Author and Year	Study Design	Number of Subjects	Indication	Hiprex dose	Outcome Measures	Findings
Furness 1975 	RCT	226	Pregnant with asymptomatic bacteriuria	1 g BID for ≥7 days vs methenamine mandelate 1 g QID vs no treatment	Symptomatic UTI, adverse events	
 
No significant difference in symptomatic UTI
 
No relevant adverse events
 

Gundersen 1986 	RCT	50	Post-menopausal	1 g BID for 6 months vs placebo	Symptomatic UTI, bacteriuria, adverse events	
 
Decrease in symptomatic UTI with HX
 
Side-effects of nausea and rash
 

Hoivik 1984 	RCT	52	Pre-menopausal	1 g QD or BID vs placebo (duration of treatment unknown)	Symptomatic UTI, adverse events	
 
Decrease in symptomatic UTI with HX
 
Side-effect of bladder stinging
 

Knoff 1985 	RCT	64	After gynecological operations requiring short-	2 g BID for 7 days vs placebo	Symptomatic UTI, bacteriuria, adverse events	
 
Decrease in symptomatic UTI with HX (3.2% of HX vs
 

			term catheterization			27.6% of placebo) 
 
Decrease in bacteriuria with HX (3.2% of HX vs 41.4% of placebo)
 
Side-effects of sore throat
 

Ladehoff 1984 	RCT	300	After gynecological operations requiring short-term catheterization	500 mg BID for 8-13 days vs no treatment	Bacteriuria, adverse events	
 
Decrease in bacteriuria with HX (30.3% of HX vs 45.6% of no treatment)
 
Side-effect of nausea
 

Parvio 1976 	Case series	52	Post-menopausal with RUTIs who are hospitalized > 2 years	No treatment for 6 months then HX 1 g BID for 6 months	Symptomatic UTI, side-effects	
 
Decrease in UTI reinfections with HX (17 cases without HX vs unknown number while on HX)
 
Side-effects of "soreness of the mouth" and abdominal pain
 

Schiotz 2002 	RCT	150	After gynecological operations requiring short-term catheterization	1 g BID for 5 days vs placebo	Symptomatic UTI, bacteriuria	
 
Decrease in symptomatic UTI with HX (2.7% of HX vs 13.9% of placebo)
 
No significant difference in bacteriuria
 
Side-effects of nausea and rash
 

Thomlinson 1968 	Quasi-RCT	130	After gynecological operations requiring catheterization	1 g BID with sodium acid phosphate 2g TID for 7 days vs no treatment	Bacteriuria, side-effects	
 
No significant difference in bacteriuria
 
No side-effects
 

Tyreman 1986 	RCT	109	After gynecological operations requiring short-term catheterization	1 g TID for 5 days vs no treatment	Symptomatic UTI, bacteriuria, adverse events	
 
Decrease in symptomatic UTI (2.2% of HX vs 28.6% of no treatment)
 
Decrease in bacteriuria with HX (9.8% of HX
 

						vs 37.9% of no treatment) • No side-effects
--	--	--	--	--	--	--

### 3. Concise Summary of Project:

#### Study Design:

[figure not shown]
There will be two parts to this project. Part 1 will be a prospective assessment of the urinary effects of Hiprex in women with RUTIs, such as acidity and concentration of formaldehyde, to determine the best oral concentration to inhibit bacterial growth in urine for each enrolled patient. Part 2 will be a long-term assessment of Hiprex on RUTI evolution in women with a longstanding history of RUTIs, with Hiprex taken at a proper dosing (as established in Part 1) and with regular urine checks at subsequent visits up to one year of follow-up.

Part 1: Women between age 50 and 85 presenting to the outpatient UTSW Urology clinic who are currently taking Hiprex (or any methenamine-containing product) or are willing to be started on Hiprex and do not meet exclusion criteria (see below) will be invited to participate in the study. During their first study visit (V1), they will be consented for this long-term prospective study. The documentation of RUTI based on the current definition of 3 documented and treated UTIs in the past year or 2 in the past 6 months will be recorded. A 3 day diary with recordings of urine pH before each meal and before bed will be obtained to document that the patient has consistent low urine pH (<6), a critical condition for methenamine conversion to formaldehyde. Then the patient will be asked to take a tablet of Hiprex 1gm and to provide one subsequent urine samples at 1 hour after the intake of Hiprex. These midstream urine samples will be processed and transferred to our Lab on campus (K2 building) before being sent to our partnering lab at UTD run by [name] for testing, including urine pH testing, and the measurements of methenamine and aldehyde produced in these urine samples.

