#### Recruitment:

All patients will be recruited from the urology practice of the PI (WCB3 4th floor).

As part of a pilot study, we plan on enrolling 100 patients over 18 months to gather sufficient data to power a more extensive randomized control trial later on, using either a placebo or a competitive low-dose antibiotic, such as Macrobid or Septra, based on the efficacy of Hiprex given at the proper dosing and in the right urinary pH milieu in this small cohort of RUTI women. The PI is raising the enrollment goal due to COVID being tentatively over and the team is able to recruit more subjects due to this.

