#### Follow-up:

Patients will be asked to return to clinic for 3 follow-up visits at: 3 months (V1), 6 months (V2), and 12 months (V3) after starting Hiprex. This research visit timing corresponds to standard-of-care clinic visits include those at 3 months, 6 months, and 12 months.

At each of these visits, patients will be asked to withhold their first dose of Hiprex until they arrive to clinic. Urine samples will be collected at baseline, then 1 hours after the dose intake. These samples will be tested according to the same protocol in the lab of [name]. In addition, patients will be administered a UTI Symptom Assessment (UTISA) questionnaire and queried about any UTI symptoms and Hiprex-associated symptoms since their last visit. If the concentration of methenamine/formaldehyde in the urine sample is found to be inadequate for bacteriostatic or bactericidal activity, the dosage might be increased to 1.5 PO BID, and/or diet-adjustment might be considered to decrease urine pH if found to be not sufficiently acidic. For patients unable to reach appropriate low pH urinary levels after the above modifications, they will be removed from the study and will not continue with the longitudinal portion.

Data:

The dataset will be extracted from EPIC and will include demographic data (age, gender, race, height, weight) as well as culture data from prior urinary tract infections, comorbid conditions (i.e. diabetes, renal insufficiency, etc.), hormonal status, methenamine usage history, and urological history (including possible surgical interventions). See Excel document.

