## **6. Criteria for Inclusion of Subjects:**

- a. Female
- b. Age 50 – 85
- c. Have RUTIs (at least 2 UTIs within the past 6 months or 3 within the past year)

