## 14. Biostatistics:

Since this is a pilot study, our goal is to enroll 100 patients with RUTIs willing to be closely monitored for 1 year on Hiprex once the appropriate dosing has been confirmed. The acquired data will inform power calculations for a future randomized control trial.

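### Urine pH below 6 is a documented condition but not an entry criterion, and women who cannot reach low pH are removed, so the 1-year UTI rate may be selected on pH after enrolment

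*Combined protocol and SAP*

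**What the plan says.** All references are to the combined protocol and SAP.

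- **Section 3, Study Design, Part 1.** After consent, each woman records urine pH for 3 days, before each meal and at bedtime. The purpose is to "document that the patient has consistent low urine pH (<6), a critical condition for methenamine conversion to formaldehyde". The test tablet follows. The text does not define 'consistent' or say what happens if the diary does not show it.
- **Section 6, inclusion.** The criteria are female sex, age 50 to 85, and "Have RUTIs (at least 2 UTIs within the past 6 months or 3 within the past year". There is no pH item. The exclusion list in Section 7 has none either.
- **Section 4, Follow-up.** For women already in follow-up, "diet-adjustment might be considered to decrease urine pH if found to be not sufficiently acidic". Women who still cannot get to a suitably low pH leave the study and do not go on with its longitudinal part. No numeric threshold is given there.
- **Section 3, primary outcome.** The number of UTI events over the 1-year study period. No analysis population is named, and nothing is said about women who were removed.
- **Section 14.** The data are to inform power calculations for a later randomised trial.
- **Section 2.** An earlier study by the same group in post-menopausal women "identified an average urine pH around 6.0 with daily variability in several patients".

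**The concern.** The same variable, urine pH, appears in three roles: a condition to be documented at the start, something that may be modified during treatment, and a reason for leaving the study. It is missing from the one place where the population is defined. Two teams following this text could produce different cohorts.

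The removal step matters most for the analysis. It acts after enrolment and after treatment has begun, on a variable that the protocol itself regards as decisive for whether the drug can work. If the UTI rate is computed only in women who stay, it describes women who were acidic or could be made so. If it is computed in everyone enrolled, it describes women aged 50 to 85 with recurrent UTI. The two rates, and their variances, need not agree. A later trial could be planned on one while enrolling the other.

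**Working it through.** **1. What there is to reproduce.** The protocol gives no alpha, power, effect size, UTI rate, SD or dropout. The target of 100 therefore cannot be reproduced or refuted. The question is how many women the pH rule could touch, and what removal does to the rate.

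**2. Populations the text allows.**

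| Reading | Women behind the 1-year rate |
|---|---|
| Diary is an entry condition | Women with low pH at the start, less any removed later |
| Diary is a record; removed women not counted | Women acidic at entry or after modification |
| Diary is a record; everyone counted | All enrolled women |

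**3. Share of women below pH 6.**

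*Inputs from the protocol:* mean pH about 6.0 (Section 2); 3 days × 4 readings = 12 readings, taking three meals a day (Section 3).

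*Assumed, because the protocol gives no SD:* normal distributions, between-woman SD (sb) 0.3 to 0.7, within-woman SD (sw) 0.2 to 0.5.

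*Formulas:*
- Share of women whose own mean is below 6: Φ((6 − μ)/sb). With μ = 6.0 this is Φ(0) = 0.50 for any sb. By symmetry the same holds for the 12-reading diary mean.
- For a woman with mean m, each reading is below 6 with probability p = Φ((6 − m)/sw). The share with all 12 readings below 6 is the average of p¹² over m. The share with at least 10 of 12 is the average of P(Bin(12, p) ≥ 10).

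*Results at μ = 6.0:*

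| Reading of 'consistent' | Share qualifying |
|---|---|
| Mean below 6 | 50% |
| At least 10 of 12 readings below 6 | 14% to 41% |
| All 12 readings below 6 | 2% to 32% |

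*Sensitivity to the mean:* for μ from 5.7 to 5.9, the share of women with their own mean below 6 is 56% to 84%. For μ = 6.1 it is 37% to 44%.

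These are shares at the diary. They are not the share removed, which depends on how many women respond to modification. The protocol gives no figure for that.

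**4. Consequence for numbers.** If the diary were an entry condition and the 100 were counted after it, the number to consent is 100/share: 100/0.5 = 200, or 100/0.2 = 500. If 100 are enrolled on Section 6 and only some contribute, the 95% half-width for the rate is 1.96 × √(rate/n) (Poisson). At an assumed 2 UTIs per year:
- n = 100: 1.96 × √(2/100) = 0.28
- n = 50: 1.96 × √(2/50) = 0.39
- n = 30: 1.96 × √(2/30) = 0.51

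**5. Consequence for the rate, illustration only.** Suppose 50 women stay acidic with 1.5 UTIs per year, and 50 do not, with 3 per year. Both rates are invented; the protocol gives no rate by pH. Suppose the second group is removed at the 6-month visit.
- Everyone followed to 12 months at unchanged rates: (50 × 1.5 + 50 × 3)/100 = 2.25 per year.
- Events and person-time to removal: (50 × 1.5 + 50 × 3 × 0.5)/(50 + 25) = 150/75 = 2.00 per year.
- Completers only: 1.50 per year.

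If the two groups had the same rate, all three figures would coincide. The size of the gap is therefore unknown, but the order shows why full follow-up is preferable to stopping the count at removal, and why either is preferable to completers only.

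**The case against.** The strongest reply is that one sequence fits every section: enrol on Section 6, record pH by diary, modify where needed, and remove those who cannot reach a low pH. Part 1's own eligibility sentence has no pH item, which agrees with Sections 6 and 7. The diary comes after consent and carries no stated penalty. On this reading nothing is contradicted. That stands, so a reader who infers a direct contradiction goes further than the text. The study-design figure is also not shown and may contain a screening step.

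It can also be said that the intended target is stated: Recruitment in Section 3 ties the later trial to efficacy in a suitable urinary pH. That is a fair account of intent. It does not say how removed women enter the rate, and it does not supply the rate in all enrolled women that a trial enrolling on Section 6 would need.

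Two further inferences are tempting and not supported:
- **A conflict over when the 100 are counted.** Recruitment says "we plan on enrolling 100 patients over 18 months to gather sufficient data to power a more extensive randomized control trial later on" and Section 14 says "our goal is to enroll 100 patients with RUTIs willing to be closely monitored for 1 year on Hiprex". Both count at enrolment.
- **An acidic minority.** This depends on a strict reading of 'consistent', on assumed SDs, and on a mean that the protocol gives only as around 6.0. That mean comes from post-menopausal women, not stated to have recurrent UTI or to be taking Hiprex, whereas current users may enrol here. At slightly lower means most women qualify on their average.

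**Conclusion.** The point holds as a gap in reconciliation with a consequence for the primary result. A documented pH condition, criteria lists without it, and a removal rule during follow-up together allow a 1-year UTI rate that is selected on pH after enrolment. That rate is among the data meant to inform the sizing of the later trial.

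The number of women concerned could be substantial: about half by diary mean if the population mean is exactly 6.0 and the distribution is symmetric, with fewer qualifying under stricter readings. The SDs, the UTI rates and the normal model are assumptions. Neither the share removed nor the difference in UTI rate by pH can be derived from the protocol. A reader might infer that the later trial will therefore expect too large an effect. The documents give no effect size and no rate by pH, so the direction is plausible but not shown.

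**What to change.** 1. Reconcile Section 3 (Part 1), Section 4 (Follow-up) and Section 6 on whether the diary pH is an entry condition or a recorded baseline value. If it is an entry condition, put it in Section 6 and say how many readings make it 'consistent'. Which clinical rule to adopt is for the investigators; this review takes no position on it.
2. Report the primary UTI rate in all enrolled women, and separately by baseline diary pH (mean below 6 versus 6 or above).
3. Continue to collect UTI events to 12 months in women removed for pH. If that is not possible, count their events and person-time up to removal, and report how many were removed, by diary pH. Only with continued collection does the rate cover a full year in everyone enrolled. Step 3 concerns outcome data only, not treatment.

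The cost is some protocol wording, one more table from diary data already planned, and continued event collection from records or the standard-of-care visits at 3, 6 and 12 months. The overall rate may look less favourable than one restricted to women with acid urine.
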